18. PROTOCOL DEVIATIONS

Any deviation from this protocol will be reported to the IRB.

19. CONSENT PROCESS

To protect participant confidentiality, we will conduct all research-related discussions and informed consent procedures in a private setting. The consent process will be completed either in person or remotely by using an electronic consent document and collection of an electronic signature with REDCap or other electronic signature service like Adobe DocuSign. The study coordinator will review the Informed Consent in person, by phone or in Zoom during the remote informed consent discussion.

The study procedures, risks, and benefits will be discussed and the study team will answer all questions prior to obtaining consent. The person performing the Informed Consent process, will ask questions of the study subject to confirm understanding and comprehension of the study. All versions of the consent forms will be approved by the relevant ethics committees prior to study initiation.

STU#: STU00214445

Eligible participants who do not wish to participate in this study will continue to receive care according to local clinical standards.

20. NON-ENGLISH-SPEAKING PARTICIPANTS

Non-English-speaking participants may be enrolled if the study team acquires an official translation of the approved informed consent form or performs consent with a translator and completes the accompanying short form in the participant's native language.

The research team will only enroll non-English speaking participants if a member of the study team is a fluent or native speaker of their language and assigned to them specifically. This is to ensure that continued support, clear communication and study training is possible for all study participants.

21. GOOD CLINICAL PRACTICE

The current study will be conducted in compliance with the protocol, International Conference on Harmonization Good Clinical Practice (ICH-GCP), and the applicable regulatory requirements. Study personnel involved in conducting this study will be qualified by education, training, and experience to perform their respective task(s) in accordance with GCP.

22. INSTITUTIONAL REVIEW BOARD (IRB)

All relevant documents for this study will be submitted to an appropriate Institutional Review Board (IRB) for review. A signed and dated letter documenting IRB approval must be obtained prior to entering participants at the site. IRBs must be constituted and their authority delegated through the institution's normal process of governance according to applicable regulatory requirements for each participating site. Each participating institution must provide for the review and approval of this protocol and the associated informed consent documents and relevant participant materials by an appropriate IRB. For each participating site, the protocol and associated informed consent and relevant participant materials will be submitted for approval to the local IRB, as per site local regulatory policies and procedures. The study will not commence at any site until initial approval is obtained from the designated IRB and an approval to enroll notification is released to the site.

The investigators must obtain approval from the IRB for all protocol amendments and, when warranted, changes to the informed consent document and/or participant materials. Protocol and informed consent form amendments can be made only with the prior approval from the PI. The investigator may not implement any protocol deviation except where necessary to eliminate an immediate hazard to study participants, or when change(s) involve only logistical or administrative aspects of the trial, i.e., change of monitor(s) or telephone number(s) (ICH 4.5.2). The investigator shall notify the IRB of deviations from the protocol or serious adverse events occurring at the site.

STU#: STU00214445

APPENDIX A - SLEEP DIARY

ID/NAME:

| | SAMPLE | |
|--|--|---|
| Today's Date | 2/25/2021 | |
| 1. What time did you get into bed? | 10:15 p.m. | |
| 2. What time did you try to go to sleep? | 11:30 p.m. | |
| 3. How long did it take you to fall asleep? | 55 min. | |
| 4. How many times did you wake up, not counting your final awakening? | 6 times | |
| 5. In total, how long did these awakenings last? | 2 hours 5 min. | |
| 6a. What time was your final awakening? | 6:35 a.m. | |
| 6b. After your final awakening, how long did you spend in bed trying to sleep? | 45 min. | |
| 6c. Did you wake up earlier than you planned? |  Yes  No |  Yes  No |
| 6d. If yes, how much earlier | 1 hour | |
| 7. What time did you get out of bed for the day? | 7:20 a.m. | |
| 8. In total, how long did you sleep? | 4 hours 10 min. | |
| 9. How would you rate the quality of your sleep? |  Very poor  Poor  Fair  Good  Very good |  Very poor  Poor  Fair  Good  Very good |
| 10. How rested or refreshed did you feel when you woke-up for the day? |  Not at all rested  Slightly rested  Somewhat rested  Well-rested  Very well-rested |  Not at all rested  Slightly rested  Somewhat rested  Well-rested  Very well-rested |
| 11a. How many times did you nap or doze? | 2 times | |
| 11b. In total, how long did you nap or doze? | 1 hour 10 min. | |
| 12a. How many drinks containing alcohol did you have? | 3 | |
| 12b. What time was your last drink? | 9:20 p.m. | |
| 13a. How many caffeinated drinks (coffee, tea, soda, energy drinks) did you | 2 drinks | |
| 13b. What time was your last drink? | 3:00 p.m. | |
| 14a. Did you take any over-the counter or prescription medication(s) to help you sleep? |  Yes  No |  Yes  No |
| 14b. If yes, list medication(s), dose, and time taken. | Medication(s): Relaxo-Herb Dose: 50 mg Time(s) taken: | Medication(s): Dose: Time(s) taken: |
| 15. Comments (if applicable) | I have a cold | |

STU#: STU00214445

**APPENDIX B –
APNEAS ANNE Sleep Sensor Survey**

Subject #: _____

Date: ____/____/____

Thank you for participating in wearing the ANNE Sleep system. This survey helps researchers better understand your experience with wearing sensors and helps develop and improve them for future patients. Please provide one answer to each of the following questions. You can skip any questions you do not know the answer to or do not want to answer.

1. Overall, all of the the sleep study sensors were comfortable for me to sleep with:
 Strongly Agree Agree Neither agree or disagree Disagree Strongly Disagree

2. Overall, ANNE Sleep sensors were comfortable for me to sleep with:
 Strongly Agree Agree Neither agree or disagree Disagree Strongly Disagree

3. How quickly you fell asleep comparing to typical nights for you
 Much Slower Slower About the same Faster Much Faster

4. The ANNE Sleep Sensors would be more comfortable to other sleep sensors
 Strongly Agree Agree Neither agree or disagree Disagree Strongly Disagree

5. The **application** of the ANNE Sleep Sensors was easy and comfortable.
 Strongly Agree Agree Neither agree or disagree Disagree Strongly Disagree

6. The **removal** of the ANNE Sleep Sensors was easy and comfortable.
 Strongly Agree Agree Neither agree or disagree Disagree Strongly Disagree

7. Using wireless ANNE Sleep Sensors would be easy to do at home.
 Strongly Agree Agree Neither agree or disagree Disagree Strongly Disagree

8. Please describe how the **wireless Chest sensor** felt while sleeping.

STU#: STU00214445

Very uncomfortable Uncomfortable No change Comfortable Very comfortable

9. Please describe how the **wireless Limb sensor** felt on your finger while sleeping.

Very uncomfortable Uncomfortable No change Comfortable Very comfortable

10. Please indicate if you experienced the following while wearing the **wireless sensors**:

Redness Irritation Both None

11. Having my sleep data collected at home and sent to my doctor would be more convenient for me.

Strongly Agree Agree Neither agree or disagree Disagree Strongly Disagree

12. I could see myself using ANNE Sleep at home to monitor my breathing while I sleep.

Strongly Agree Agree Neither agree or disagree Disagree Strongly Disagree

13. Please provide any other thoughts about the concerns or benefits of wireless monitoring:

STU#: STU00214445

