4.1 Primary Outcome Measures

- Analysis of variation between nights of AHI derived from ANNE Sleep system across multiple sleep nights at home
- Analysis of agreement for diagnosis of moderate to severe OSA by determining a patient's Apnea-Hypopnea Index (AHI) wearing the ANNE Sleep system and WatchPAT ONE over one (1) night worn concurrently
- Patient responses on psychometric surveys for comfort and usability comparing ANNE Sleep and WatchPAT ONE

•

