10.2 Apnea-hypopnea index (AHI) and oxygen desaturation index (ODI)

1. AHI will be calculated in ranges of 15 – 30 apnea/hypopnea events per hour for moderate OSA and ≥ 30 apnea/hypopnea events per hour for severe OSA. Continuous variables of AHIs during ~~three~~four-night study will be summarized using tables of descriptive statistics. The AHIs with variables will be summarized using counts and percentages. Descriptive statistics will be presented by diagnosis.
2. Diagnostic outcomes will be tabulated and compared for ANNE Sleep vs WatchPAT ONE.
3. Patient preference will be elicited via psychometric surveys for comfort and usability comparing ANNE and WatchPAT ONE.

STU#: STU00214445

4. The oxygen desaturation index (ODI), the hourly average number of desaturation episodes, will also be calculated.

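### Appendix B has no item that measures experienced ease of use apart from comfort: items 5 and 6 merge the two, and items 4 and 7 are hypothetical

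*Combined protocol and SAP*

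**What the plan says.** Section 4.1 lists as its third primary outcome: "Patient responses on psychometric surveys for comfort and usability comparing ANNE Sleep and WatchPAT ONE". For its analysis, Section 10.2, item 3, says only: "Patient preference will be elicited via psychometric surveys for comfort and usability comparing ANNE and WatchPAT ONE". No scoring rule or item-level analysis of the survey is given.

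The survey is Appendix B, with 12 closed items and one open item. The parts that matter here are:

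- Items 5 and 6 state that the application and the removal, respectively, "of the ANNE Sleep Sensors was easy and comfortable".
- Item 7: "Using wireless ANNE Sleep Sensors would be easy to do at home".
- Item 4: "The ANNE Sleep Sensors would be more comfortable to other sleep sensors".
- Item 2: "Overall, ANNE Sleep sensors were comfortable for me to sleep with". Item 1 puts the same statement about all of the sensors worn.
- Items 8 and 9 ask how the chest and limb sensors felt, on a five-point scale from very uncomfortable to very comfortable with 'No change' in the middle.

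On timing, Section 8.1.2 has subjects set up both devices on Night One and ANNE Sleep alone on Nights 2 to 4. Section 8.1.3 has them apply the ANNE sensors themselves. Section 8.2 and the schedule of events place the usability survey at the end, after data collection.

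**The concern.** The outcome names two attributes, comfort and usability, so the form should let each be reported. A statement that joins ease and comfort gives one answer for both. Someone who found application easy but uncomfortable can disagree or choose the midpoint, but the reader cannot then tell which attribute failed. A 'would be' item asked after home use records expectation where experience is available.

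If these items are the only ones that touch ease, the study ends with no measurement of experienced ease of use on its own. Analysis cannot recover it, because the separate answers were never collected.

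A second, lesser matter is that every agree/disagree statement is worded favourably. A subject who tends to agree whatever the content would push each of those items the same way, and more subjects would not reduce that.

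**Working it through.** The plan gives no figure for the survey (no effect size, SD, alpha or power), so there is nothing to reproduce. The check is a coding of Appendix B, followed by two illustrations on assumed values.

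**Step 1. Coding of the 12 closed items.**

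| Items | Format | Wording | Tense | Content |
|---|---|---|---|---|
| 1 | agree/disagree | favourable | experience | comfort, all sensors |
| 2 | agree/disagree | favourable | experience | comfort, ANNE |
| 3 | two-directional | neutral | experience | speed of falling asleep |
| 4 | agree/disagree | favourable | hypothetical | comfort against other sensors |
| 5, 6 | agree/disagree | favourable | experience | ease and comfort together |
| 7 | agree/disagree | favourable | hypothetical | ease at home |
| 8, 9 | two-directional | neutral | experience | comfort, by sensor |
| 10 | tick list | neutral | experience | redness, irritation |
| 11 | agree/disagree | favourable | hypothetical | convenience of home collection |
| 12 | agree/disagree | favourable | prospective | willingness to use ANNE |

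Agree/disagree items: 8 of 12. Favourably worded: 8 of 8. Reverse-worded: 0 of 8.

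**Step 2. Where each attribute is measured.** Ease appears in items 5, 6 and 7 only. Items 5 and 6 merge it with comfort, and item 7 is hypothetical. Experienced ease on its own: 0 items. Experienced comfort of ANNE on its own: 3 items (2, 8, 9). Device-to-device comparison: 1 item (4), and it is hypothetical.

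**Step 3. Whether another form fills the gap.** Appendix A is a sleep diary. Appendix C, which Section 8.2 cites for the closing surveys, covers demographics, medical history and sleep. Neither asks about ease of using a device.

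**Step 4. What a two-part answer can hide (assumed values).** Suppose a share p = 0.80 found application easy and q = 0.60 found it comfortable.

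- Subjects agree only if both hold: from max(0, p + q − 1) = 0.40 to min(p, q) = 0.60. Under independence, 0.80 × 0.60 = 0.48.
- Subjects agree if either holds: from max(p, q) = 0.80 to min(1, p + q) = 1.00. Under independence, 0.80 + 0.60 − 0.48 = 0.92.

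Under the literal reading the range is 40% to 60%, and it reveals neither the 80% nor the 60%. A span of 40% to 100% arises only if some readers take 'and' as 'or'.

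**Step 5. What agreement bias could add (assumed values).** If a share a agrees whatever the content, observed agreement is a + (1 − a)p. With p = 0.60:

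- a = 0.05: 0.05 + 0.95 × 0.60 = 0.62
- a = 0.15: 0.15 + 0.85 × 0.60 = 0.66

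That is a shift of 2 to 6 points. For scale, the exact 95% confidence interval for 18 of 30 (60%) is 41% to 77%.

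**The case against.** A reader might infer that the usability answers as a whole cannot be interpreted, or that the form is shown to lean towards ANNE. The documents support neither.

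- Only 2 of the 12 closed items merge two attributes. Items 2, 3, 8, 9 and 10 each ask about one thing, as experienced, and item 13 invites concerns as well as benefits.
- Agreeing with item 1 does not favour ANNE in particular, because on Night One the sensors worn include WatchPAT ONE. Item 11, "Having my sleep data collected at home and sent to my doctor would be more convenient for me", names no device.
- Nothing in the documents shows that agreement bias exists here or how large it is. Items 8 and 9 have neutral stems and list the negative option first, so comparing them with item 2 gives a partial check.
- Expected ease and willingness to use a device again are legitimate acceptability questions, and experience is already asked in items 1, 2, 5 and 6.
- No test, score or threshold hangs on the survey, and better wording would not by itself supply parallel ratings of WatchPAT ONE.

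All of this stands as a limit on the point. It does not close the gap on ease: item 5 covers ease of application only jointly with comfort, item 7 is an expectation, and the check from items 8 and 9 applies to comfort alone. Item 12 already asks about future use, so moving items 4 and 7 to the past tense does not remove that topic.

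**Conclusion.** The point holds in a limited form. Appendix B contains no item that measures experienced ease of use separately from comfort, although the third primary outcome names both comfort and usability. Its only device-to-device item asks for expectation when experience is at hand. This follows from the item wording and the schedule and needs no assumption.

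The comfort items 2, 8 and 9, and items 3 and 10, remain interpretable. The six agree/disagree items that name ANNE (2, 4, 5, 6, 7, 12) are open to agreement bias in its favour, with a partial check for comfort and none for ease. The percentages in Steps 4 and 5 rest wholly on assumed shares. They show how the faults act and do not estimate their size in this trial. The AHI outcomes and safety are not affected. This is a cheap improvement worth making, because the missing answers cannot be recovered later.

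**What to change.** Before the form is first used:

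1. Split items 5 and 6 into separate ease and comfort items for application and for removal, preferably on two-directional scales like those of items 8 and 9 (very difficult to very easy; very uncomfortable to very comfortable).
2. Reword items 4 and 7 in the past tense, about the study nights.
3. State in Section 10.2 that ease and comfort will be reported separately.

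Optionally, relabel the 'No change' midpoint of items 8 and 9 as 'neither comfortable nor uncomfortable', since nothing on a comfort scale has changed.

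The cost is two more items, a minor IRB amendment, and loss of direct comparability with any earlier use of the same form. Items 1, 2, 4, 7, 11 and 12 would still be favourably worded agree/disagree statements, so their results should be read with that in mind.

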APPENDIX C – DEMOGRAPHIC, MEDICAL HISTORY AND SLEEP DIARY

| Field Label | Choices, Calculations, OR Slider Labels |
|---|---|
| 
In order to ensure that this research serves all people living in the U.S., we need to ask you how identify your ethnic and racial background. This information will remain confidential, and will not affect your participation in the study in any way. It will only be used for reporting general demographics or statistics.
 | |
| 
The following questions are about your demographic background:
 | |
| Gender | 1, Male 2, Female |
| Race: | 1, American Indian or Alaska Native 2, Asian 3, Native Hawaiian or Pacific Islander 4, Black or African American 5, White 6, More than once race 7, Choose not to answer |
| Ethnicity: | 1, Hispanic or Latino 2, Non-Hispanic or Latino 3, Choose not to answer |
| Highest Education Level completed: | 1, Never attended school or only attended kindergarten 2, Grades 1 through 8 (Elementary) 3, Grades 9 through 11 (Some high school) 4, Grade 12 or GED (High school graduate) 5, College 1 year to 3 years (Some college or technical school) 6, College 4 years of more (College graduate) |
| Current Marital Status: | 1, Married 2, Single 3, Widowed 4, Divorced/Separated 5, Domestic partner |
| Current Employment Status: | 1, Employed 2, Unemployed 3, Retired 4, Retired due to disability |
| 
The following questions are about your Health:
 | |
| Date of last medical exam: | |
| Sleep Provider: | |
| Location: | 1, Northwestern Memorial Hospital (Downtown) 3, Central DuPage Hospital (CDH) 4, Northwestern Medical Group (NMG) |
| Height: | |
| Weight: | |
| 
Are you currently diagnosed or do you have a history of any cardiovascular disorders?
 | |
| Please select all that apply: | 1, Hypertension (high blood pressure) 2, Congenital heart disease (malformations of heart structure existing at birth) 3, Arrhythmia (abnormal heart rhythm) 4, Coronary artery disease (narrowing of the arteries) 5, Deep vein thrombosis (blood clot in lower extremities) 6, Pulmonary embolism (blood clot in the lungs) 7, Heart attack 8, Heart failure 9, Cardiomyopathy (heart muscle disease) 10, Other |
| If other, please explain: | |
| 
If you selected any of the above disorders, please include dates of diagnosis and current status (ongoing or resolved). If resolved, please include end date:
 | |

STU#: STU00214445

| | |
|---|--|
| Are you currently diagnosed or do you have a history of any pulmonary or respiratory system disorders? | |
| Please select all that apply: | 1, Asthma 2, Chronic Obstructive Pulmonary Disease (COPD) 3, Chronic Bronchitis 4, Lung Cancer 5, Pneumonia 6, Emphysema 7, COVID-19 8, Pleural Effusion (collection of fluid between the lung and chest wall) 10, Other |
| If other, please explain: | |
| If you selected any of the above disorders, please include dates of diagnosis and current status (ongoing or resolved). If resolved, please include end date: | |
| Are you currently diagnosed or do you have a history of any gastrointestinal (GI) disorders? | |
| Please select all that apply: | 1, Acid reflux 2, Heartburn 3, GERD 4, Crohn's disease 5, Ulcerative colitis 6, Irritable Bowel Syndrome (IBS) 7, Peritonitis 8, Fibrosis and cirrhosis of liver 9, Cholecystitis 10, Other |
| If other, please explain: | |
| If you selected any of the above disorders, please include dates of diagnosis and current status (ongoing or resolved). If resolved, please include end date: | |
| Are you currently diagnosed or do you have a history of any endocrine system disorders? | |
| Please select all that apply: | 1, Hyperthyroidism 2, Hypothyroidism 3, Thyrotoxicosis 4, Hypoparathyroidism 5, Type I Diabetes 6, Type II Diabetes 7, Adrenal disorder 8, Cushing's syndrome 10, Other |
| If other, please explain: | |
| If you selected any of the above disorders, please include dates of diagnosis and current status (ongoing or resolved). If resolved, please include end date: | |
| Are you currently diagnosed or do you have a history of any neurological disorders? | |
| Please select all that apply: | 1, Dementia 2, Huntington's Disease 3, Parkinson's Disease 4, Alzheimer's Disease 5, Bell's Palsy 6, Cerebral Aneurysm 7, Epilepsy or Seizures 8, Fibromyalgia 9, Amyotrophic Lateral Sclerosis (ALS) 10, Other |
| If other, please explain: | |
| If you selected any of the above disorders, please include dates of diagnosis and current status (ongoing or resolved). If resolved, please include end date: | |
| Are you currently diagnosed or do you have a history of any sleep disorders? | |
| Please select all that apply: | 1, Insomnia 2, Restless Leg Syndrome 3, Parasomnia 4, Sleep Apnea (confirmed diagnosis) 5, Narcolepsy 10, Other |
| If other, please explain: | |
| If you selected any of the above disorders, please include dates of diagnosis and current status (ongoing or resolved). If resolved, please include end date: | |

STU#: STU00214445

| | |
|---|---|
| Are you currently diagnosed or do you have a history of any psychiatric or psychological disorders? | |
| Please select all that apply: | 1, Bipolar disorders 2, Depression 3, Anxiety 4, Post-traumatic stress disorder (PTSD) 5, Schizophrenia 6, Personality disorders 10, Other |
| If other, please explain: | |
| If you selected any of the above disorders, please include dates of diagnosis and current status (ongoing or resolved). If resolved, please include end date: | |
| Are you currently diagnosed or do you have a history of any lymphatic or hematologic disorders? | |
| Please select all that apply: | 1, Lymphedema 2, Hodgkin's Lymphoma 3, Non-Hodgkin's Lymphoma 4, Anemia 5, Sickle cell 6, Leukemia 10, Other |
| If other, please explain: | |
| If you selected any of the above disorders, please include dates of diagnosis and current status (ongoing or resolved). If resolved, please include end date: | |
| Are you currently diagnosed or do you have a history of any skin or dermatological disorders? | |
| Please select all that apply: | 1, Acne 2, Hives 3, Rosacea 4, Eczema 5, Psoriasis 6, Melanoma 10, Other |
| If other, please explain: | |
| If you selected any of the above disorders, please include dates of diagnosis and current status (ongoing or resolved). If resolved, please include end date: | |
| Are you currently diagnosed or do you have a history of any musculoskeletal disorders? | |
| Please select all that apply: | 1, Carpal tunnel 2, Arthritis 3, Osteoporosis 4, Tension Neck Syndrome 5, Tendonitis 6, Broken bone 7, Tendon or Ligament Sprain 8, Torn Rotator Cuff 9, Ruptured or Herniated Disc 10, Other |
| If other, please explain: | |
| If you selected any of the above disorders, please include dates of diagnosis and current status (ongoing or resolved). If resolved, please include end date: | |
| Do you have a history of any allergies? This can include seasonal, skin, food, or drug/medicine allergies. | |
| Please list allergies here, including start dates and current status (ongoing or resolved). If resolved, please include end date: | |
| Do you have a history of any other medical illness? | |

STU#: STU00214445

| | |
|---|---|
| SLEEP DIARY | |
| The following questions are about your sleep last night (before study visit). | |
| Please list all other medical illnesses here, including start dates and current status (ongoing or resolved). If resolved, please include end date: | |
| 2. Did you wear CPAP Device last night? | |
| If yes, level of titration: | |
| 3. What time did you go into bed? {time_in_bed} | |
| 4. What time did you try to go to sleep? {time_sleep} {ampm} | |
| | 1, AM 2, PM |
| 5. How long did it take you to fall asleep? | |
| 6a. How many times did you wake up, not counting your final awakening? | |
| 6b. In total, how long did these awakenings last? | |
| 7a. What time was your final awakening? | |
| 7b. After your final awakening, how long did you spend in bed trying to fall back asleep? | |
| 7c. Did you wake up earlier than you planned? | |
| 7d. If yes, how much earlier? | |
| 8. What time did you get out of bed for the day? {time_up} {am_and_pm} | |
| 9. In total, how long did you sleep? | |
| 10. How would you rate the quality of your sleep? | 1, Very poor 2, Poor 3, Fair 4, Good 5, Very good |
| 11. How rested or refreshed did you feel when you woke up for the day? | 1, Not at all rested 2, Slightly rested 3, Somewhat rested 4, Well-rested 5, Very well-rested |
| 12a. How many times did you nap or doze? | |
| 12b. In total, how long did you nap or doze? | |
| 13a. How many drinks containing alcohol did you have? | |
| 13b. What time was your last drink? {time_drink}{am_pm_2} | |
| 14a. How many caffeinated drinks (coffee, tea, soda, energy drinks) did you have? | |
| 14b. What time was your last drink? {time_coffee}{am_pm_3} | |
| 15. Did you take any over-the-counter or prescription medication(s) to help you sleep? | |
| Type of medication: | |
| Dose: | |
| Time taken: | |

STU#: STU00214445

| | |
|--|--|
| Did you take any additional medications? | |
| Type of medication: | |
| Dose: | |
| Time taken: | |
| 16. Comments, if applicable: | |

STU#: STU00214445

